9 ADVERSE EVENTS AND TOXICITY MANAGEMENT

Given that subjects will receive standard of care evaluation and treatment for their chronic hepatitis C infection, we believe that study participation poses minimal excess risk. Indeed, we believe that subjects will benefit from improved access to this important treatment which will be provided at a convenient location by a known physician under the guidance of an infectious disease physician with extensive experience treating HCV infection. Potential risks to study participation may include

1. Increased frequency of appointments at the outpatient addiction clinic for those who are usually seen less frequently than every 2 weeks.
2. Increased duration of the appointments at the outpatient addiction clinic for completion of study procedures.

9.1 Definitions of Adverse Events, Adverse Reactions, and Serious Adverse Events

9.1.1 Adverse Events

An AE is any untoward medical occurrence in a clinical study subject administered a pharmaceutical product, which does not necessarily have a causal relationship with the treatment. An AE can therefore be any unfavorable and/or unintended sign, symptom, or disease temporally associated with the use of a medicinal product, whether or not considered related to the medicinal product. AEs may also include pre- or post-treatment complications that occur as a result of protocol specified procedures, lack of efficacy, overdose, drug abuse/misuse reports, or occupational exposure. Preexisting events that increase in severity or change in nature during or as a consequence of participation in the clinical study will also be considered AEs.

An AE does not include the following:

- Medical or surgical procedures such as surgery, endoscopy, tooth extraction, and transfusion. The condition that led to the procedure may be an adverse event and must be reported.
- Pre-existing diseases, conditions, or laboratory abnormalities present or detected before the Screening Visit that do not worsen
- Situations where an untoward medical occurrence has not occurred (e.g., hospitalization for elective surgery, social and/or convenience admissions)
- Overdose without clinical sequelae
- Any medical condition or clinically significant laboratory abnormality with an onset date before the consent form is signed and not related to a protocol-associated procedure is not an AE. It is considered to be pre-existing and should be documented on the medical history CRF.

9.1.2 Serious Adverse Events

A serious adverse event (SAE) is defined as an event that, at any dose, results in the following:

- Death
- Life-threatening (Note: The term “life-threatening” in the definition of “serious” refers to an event in which the subject was at risk of death at the time of the event; it does not refer to an event that hypothetically might have caused death if it were more severe.)
- In-patient hospitalization or prolongation of existing hospitalization
- Persistent or significant disability/incapacity
- A congenital anomaly/birth defect
- A medically important event or reaction: such events may not be immediately life-threatening or result in death or hospitalization but may jeopardize the subject or may require intervention to prevent one of the other outcomes constituting SAEs. Medical and scientific judgment must be exercised to determine whether such an event is a reportable under expedited reporting rules. Examples of medically important events include intensive treatment in an emergency room or at home for allergic bronchospasm; blood dyscrasias or convulsions that do not result in hospitalization; and development of drug dependency or drug abuse. For the avoidance of doubt, infections resulting from contaminated medicinal product will be considered a medically important event and subject to expedited reporting requirements.

Clarification of Serious Adverse Events:

- Death is an outcome of an adverse event, and not an adverse event in itself. In reports of death due to "Disease Progression", where no other information is provided, the death will be assumed to have resulted from progression of the disease being treated with the study drugs.
- All deaths, regardless of cause, must be reported for subjects on study and for deaths occurring within 30 days of the last study evaluation.
- "Occurring at any dose" does not imply that the subject is receiving study drug at the time of the event. Dosing may have been given as treatment cycles or interrupted temporarily prior to the onset of the SAE, but may have contributed to the event.
- "Life-threatening" means that the subject is at immediate risk of death from the event as it occurred. This does not include an event that might have led to death, if it had occurred with greater severity.
- Complications that occur during hospitalizations are AE's. If a complication prolongs hospitalization, it is an SAE.
- "Inpatient hospitalization" means the subject has been formally admitted to a hospital for medical reasons, for any length of time. This may or may not be overnight. It does not include presentation and care within an emergency department.
- The Investigator should attempt to establish a diagnosis of the event based on signs, symptoms and/or other clinical information. In such cases, the diagnosis should be documented as the AE and/or SAE and not the individual signs/symptoms

NOTE: The following hospitalizations are not considered SAEs:

- A visit to the emergency room or other hospital department lasting less than 24 hours that does not result in admission (unless considered an “important medical event” or a life-threatening event)
- Elective surgery planned before signing consent
- Admissions as per protocol for a planned medical/surgical procedure
- Routine health assessment requiring admission for baseline/trending of health status (e.g., routine colonoscopy)

- Medical/surgical admission for purpose other than remedying ill health state that was planned before study entry. Appropriate documentation is required in these cases.
- Admission encountered for another life circumstance that carries no bearing on health status and requires no medical/surgical intervention (e.g., lack of housing, economic inadequacy, caregiver respite, family circumstances, administrative).

9.1.3 Clinical Laboratory Abnormalities and Other Abnormal Assessments as Adverse Events or Serious Adverse Events

Laboratory abnormalities without clinical significance are not recorded as AEs or SAEs. However, laboratory abnormalities (e.g., clinical chemistry, hematology, and urinalysis) that require medical or surgical intervention or lead to study drug interruption, modification, or discontinuation must be recorded as an AE, as well as an SAE, if applicable. In addition, laboratory or other abnormal assessments (e.g., electrocardiogram, x-rays, vital signs) that are associated with signs and/or symptoms must be recorded as an AE or SAE if they meet the definition of an AE or SAE as described in Sections 9.1.1 and 9.1.2. If the laboratory abnormality is part of a syndrome, record the syndrome or diagnosis (e.g., anemia), not the laboratory result (i.e., decreased hemoglobin).

For specific information on handling of clinical laboratory abnormalities in this study, please refer to Section 9.5.

9.2 Assessment of Adverse Events and Serious Adverse Events

The Investigator or qualified Sub-Investigator is responsible for assessing AEs and SAEs for causality and severity, and for final review and confirmation of accuracy of event information and assessments.

9.2.1 Assessment of Causality for Study Drugs and Procedures

The Investigator or qualified Sub-Investigator is responsible for assessing the relationship to study drug treatment using clinical judgment and the following considerations:

- No: Evidence exists that the adverse event has an etiology other than the study drug. For SAEs, an alternative causality must be provided (e.g., pre-existing condition, underlying disease, intercurrent illness, or concomitant medication).
- Yes: There is reasonable possibility that the event may have been caused by the investigational medicinal product.

It should be emphasized that ineffective treatment should not be considered as causally related in the context of adverse event reporting.

The relationship to study procedures (e.g., invasive procedures such as venipuncture or biopsy) should be assessed using the following considerations:

- No: Evidence exists that the adverse event has an etiology other than the study procedure.
- Yes: The adverse event occurred as a result of protocol procedures, (e.g., venipuncture)

9.2.2 Assessment of Severity

The severity grading of AEs will be assessed as Grade 1, 2, 3, or 4 using the GSI Grading Scale for Severity of Adverse Events and Laboratory Abnormalities (Appendix 4).

For AEs associated with laboratory abnormalities, the event should be graded on the basis of the clinical severity in the context of the underlying conditions; this may or may not be in agreement with the grading of the laboratory abnormality.

9.3 Sponsor-Investigator Requirements and Instructions for Reporting Adverse Events and Serious Adverse Events

All SAEs, regardless of cause or relationship, that occur after the subject first consents to participate in the study (i.e., signing the informed consent) and throughout the duration of the study, including the protocol-required post-treatment follow-up period, will be reported to CRI as instructed. This also includes any SAEs resulting from protocol-associated procedures performed from screening onwards.

All AEs, regardless of cause or relationship, that occur from initiation of study drug until 4 weeks after last administration of study drug shall be reported to the CRF/eCRF database as instructed.

Any SAEs and deaths that occur after the Post-Treatment follow-up visit OR within 30 days of the last dose of study drug (whichever is longer), regardless of causality, shall also be reported.

All AEs should be followed up until resolution or until the adverse event is stable, if possible.

Investigators are not obligated to actively seek SAEs after the 30 day period. However, if the Investigator learns of any SAEs that occur after study participation has concluded and the event is deemed relevant to the use of study drug, he/she should promptly document and report the event for further assessment by CRI study team.

CRI has requirements for expedited reporting of serious adverse events which meet specific requirements of worldwide regulatory authorities. The reporting period begins when a subject signs the informed consent, and ends 30 days after discontinuation of dosing or completion of the subject's participation in the study if the last scheduled visit occurs at a later time. CRI and WIRB (or local IRB if not using the central IRB) will be notified within 24 hours of the Sponsor-Investigator's knowledge of an event. The procedures for Investigators and study staff reporting all serious adverse events, regardless of causal relationship, are as follows:

- Study staff notify the CRI Medical Monitor and Principal Investigator via [contact].
- The study staff will complete the IRB Promptly Reportable Information Form and MedWatch 3500A. The Principal or Sub-Investigator must sign and date the form. If only limited information is available, follow up reports are required. If the Investigator believes that an SAE is not related to the investigational product but is potentially related to the conditions of the study (such as withdrawal of previous therapy, or a complication of a study procedure), the potential relationship should be specified in the narrative section of the SAE report. If an ongoing SAE changes in its intensity or relationship to the investigational product, a follow up SAE report will be filed within 24 hours of awareness. As follow-up information becomes available, it should be sent immediately using the same procedure used for transmitting the initial SAE report. All SAEs should be followed to resolution or stabilization. The original SAE form must be kept on file at the study site.
- Record the event on the AE eCRF
- For fatal or life-threatening events, also fax copies of hospital case reports, autopsy reports, and other documents with subject personal identifying information redacted.
- Additional information may be requested to ensure the timely completion of accurate safety reports.

Any medications necessary for treatment of the SAE must be recorded onto the concomitant medication section of the subject's eCRF and the event description section of the SAE form.

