7.3 Prior and Concomitant Medications

Concomitant medications taken within 30 days prior to screening, up to and including 30 days after the last dose of study drug, need to be recorded in the source documents and case report form(s) (CRFs).

The following medications are prohibited during the screening period and for a minimum of 28 days prior to the Baseline/Day 1 Visit through the end of study:

- Proton pump inhibitors (other than omeprazole 20 mg as below)
- Amiodarone
- Digoxin
- Carbamazepine
- Phenytoin
- Phenobarbital
- Oxcarbazepine
- Rifabutin
- Rifampin
- Rifapentine
- Efavirenz

- Tipranavir/ritonavir
- Sofosbuvir as a single agent
- St. John's wort, echinacea, milk thistle
- Rosuvastatin at a dose exceeding 10 mg
- Atorvastatin at a dose exceeding 20 mg

The following medications will be used with caution during the study:

Velpatasvir solubility decreases as pH increases. Drugs that increase gastric pH are expected to decrease the concentration of velpatasvir. Therefore, patient who are currently on acid lowering therapy including Antacids (Tums, Mylanta, Maalox, Rolaids etc.), Famotidine/Pepcid, Ranitidine/Zantac, Esomeprazole/Nexium, Omeprazole/Prilosec, Lansoprazole/Prevacid, Pantoprazole/Protonix and who must continue acid lowering therapy must agree to one of the three acid lowering treatment regimens.

- Tums as needed separated from Epclusa by at least 4 hours
- Zantac at a dose no higher than 150 mg once daily to be separated from Epclusa by 12 hours
- Omeprazole at a dose no higher than 20 mg once daily. For patients on omeprazole, Epclusa must be taken with food 4 hours prior to omeprazole dosing.

Renal function should be monitored in patients taking tenofovir DF with Epclusa.

Epclusa increases levels of the HMG-CoA reductase inhibitors, rosuvastatin and atorvastatin. Patients on atorvastatin and rosuvastatin should be monitored closely for evidence of myopathy. The dose of rosuvastatin should not exceed 10 mg and the dose of atorvastatin should not exceed 20 mg.

Medications for disease conditions excluded from the protocol (e.g., active cancer, transplantation) are not listed under this Concomitant Medication section and are disallowed in the study.

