8.4.1 Post-Treatment Week 4 and 12 (+/- 5 days)

The following procedures/assessments are to be completed:

- Assessment of AEs
- Pregnancy testing for women of childbearing potential only at the Post-Treatment Week 4 visit only (Reference Study Procedures Table Appendix 2)
- Obtain blood samples (Reference Study Procedures Table Appendix 2)
- Additionally, at post treatment week 12 visit only, subject will complete Quality of Life Surveys FACT-F, PROMIS ED -Depression SF8a, SF36)

Subjects with a HCV RNA > LLOQ at the Post-Treatment Week 12 Visit will return for confirmatory HCV RNA, preferably within 2 weeks.

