10.2 Analysis Conventions

10.2.1 Analysis Sets

10.2.1.1 *Efficacy*

The analysis set for antiviral activity analyses will be subjects who were enrolled into the study and received at least one dose of study drugs.

10.2.1.2 *Safety*

The primary analysis set for safety analyses will include subjects who received at least one dose of study drug.

Treatment-emergent data will be analyzed and defined as data collected from the first dose of study drug through the date of last dose of study drug plus 30 days.

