10.6 Secondary Analysis

Adherence:

- Percentage of patients who miss 1-4% of doses, 5-9% of doses, and 10-20% of doses and > 20% of doses and the 95% confidence interval will be reported. The percentage of doses taken out of total doses prescribed will be reported with its 95% confidence interval.

Quality of Life:

- Mean in QOL scores from baseline to EOT will be reported with its 95% confidence interval.

Safety Analysis

- All safety data collected on or after the first dose of study drug administration up to 30 days after the last dose of study drug will be summarized. **All AE's of each level severity will be reported with the number and percent who experienced them. The number and percent of patients who stopped the study because of SAE's will be reported, with the 95% confidence interval.**

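### Concomitant medications must be recorded to 30 days after last dose but no review is scheduled after end of treatment, and the entry rule for non-serious AEs stops two days short of the safety analysis window

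*Combined protocol and SAP*

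**What the plan says.** **Concomitant medications.** Section 7.3 wants medications recorded in the source documents and CRFs "up to and including 30 days after the last dose of study drug". It also prohibits a list of drugs until the end of the study. Sections 8.3.1 to 8.3.4 pair AE and medication assessment at baseline, every biweekly visit, end of treatment (EOT) and early termination (ET). Section 8.4.1, for post-treatment weeks 4 and 12, lists AE assessment without medications. Appendix 2 agrees: the medication review row is marked from screening to EOT/ET and at unscheduled visits, and is blank in the post-treatment column.

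**Adverse events.** Section 9.3 requires AEs of any cause to be entered in the CRF/eCRF if they occur "from initiation of study drug until 4 weeks after last administration of study drug". Section 10.2.1.2 defines treatment-emergent data as "data collected from the first dose of study drug through the date of last dose of study drug plus 30 days", and Section 10.6 says that safety data "up to 30 days after the last dose of study drug will be summarized".

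**Serious events.** Section 9.3 treats these separately. SAEs occurring after consent and "throughout the duration of the study, including the protocol-required post-treatment follow-up period, will be reported to CRI as instructed", and the reporting steps include the instruction "Record the event on the AE eCRF".

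**The concern.** There are two separate mismatches between what the plan requires and what its procedures deliver.

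The larger is the medication record. A duty to record through day 30 has no scheduled visit at which to carry it out. Sites will either miss the requirement or improvise. The record matters because Section 9.2.1 names concomitant medication among the possible alternative causes of an SAE. The record of what a subject was taking would be thinnest just after dosing ends, which is still inside the treatment-emergent window.

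The smaller is the AE entry limit. A coordinator who follows 9.3 to the letter need not enter a non-serious AE starting on day 29 or 30, although the analysis claims to cover those days. Rates described as covering 30 days would then rest on 28 days of required entry for non-serious events.

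**Working it through.** The plan gives no figure to reproduce. The check converts each window to days after last dose (day 0) and compares them.

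**Inputs**
- Analysis window: last dose + 30 days (10.2.1.2, 10.6).
- Required AE entry: last dose + 4 weeks (9.3).
- Medication recording: last dose + 30 days (7.3).
- Last scheduled medication review: EOT at Week 12, ±3 days (8.3.3), or ET (8.3.4).
- Post-treatment visits: weeks 4 and 12, ±5 days (8.4.1).
- Treatment 12 weeks = 84 days; about 20 subjects (5.1).

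**AE entry gap**
- Last required entry day: 4 × 7 = 28.
- Gap: 30 − 28 = 2 days (days 29 and 30).
- Share of the post-dose window: 2/30 = 6.7%.
- Share of the full treatment-emergent period: 2/(84 + 30) = 2/114 = 1.8%.
- Over 20 subjects: 20 × 2 = 40 person-days.

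**Medication gap, completers**
- EOT visit on or up to 3 days before the last dose: 30 − 0 = 30 post-dose days uncovered.
- EOT visit 3 days after the last dose: 30 − 3 = 27 days uncovered.
- Range: 27 to 30 of 30 days (90% to 100%), or 20 × 27 = 540 to 20 × 30 = 600 person-days.

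**Would a week 4 review close it?**
- Week 4 visit: 28 ± 5 = days 23 to 33, which is 11 allowed days.
- Visits on days 23 to 29 come before day 30: 7 of 11 allowed days. For these, some days up to 30 remain open until the next scheduled contact.
- Week 12 visit: 84 ± 5 = days 79 to 89.
- Recall interval for days picked up at week 12: shortest 79 − 30 = 49 days; longest, after a day-23 visit, 89 − 24 = 65 days. That is roughly 7 to 9 weeks, for at most 7 days of history (days 24 to 30).

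**Prohibited-medication period**
- If the end of study is the post-treatment week 12 visit, the prohibition lasts to day 79 to 89, while the recording duty ends on day 30. The last 79 − 30 = 49 to 89 − 30 = 59 days of the prohibition have neither a recording duty nor a scheduled review.

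**The case against.** A reader might infer that AE capture ceases at 4 weeks, that the safety tables will be materially undercounted, or that no post-treatment medication data will exist. The documents do not support any of these.

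- **AE capture continues.** SAEs are reported throughout follow-up and entered on the AE eCRF. AEs of all kinds are asked about at both post-treatment visits. Section 9.3 sets what must be entered; it does not forbid entering a later event found at week 4 or week 12. Only required entry of non-serious AEs with onset on days 29 and 30 is at issue.
- **An undercount is possible, not certain.** Sections 10.2.1.2 and 10.6 speak of data collected, and can be read as a cut-off applied to whatever was entered.
- **The medication record is not empty.** Section 8.5 collects medications at unscheduled visits, 9.3 sends drugs used to treat an SAE to the medication section of the eCRF, and 9.4 asks for the treatment required for every AE. Section 7.3 itself remains a standing instruction.
- **No planned result depends on it.** Section 10 contains no concomitant medication analysis.

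All of this stands and limits the size of the point. It does not remove it. Unscheduled visits occur only on request, and the AE and SAE routes record drugs given for an event, not those that might have caused it. A general instruction in 7.3 without a matching visit item is easily missed. Nor is four weeks clearly shorthand for 30 days, since Section 9.3 uses 30 days for SAEs and deaths in the paragraph after the 4-week limit.

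**Conclusion.** Both inconsistencies are real and minor. The medication gap is the main one: 27 to 30 of the 30 days that 7.3 requires have no scheduled collection, with partial capture by other routes. The AE mismatch is 2 of 30 post-dose days, non-serious events only. SVR12 is unaffected. The primary safety endpoint in 10.1.4, an AE leading to permanent discontinuation of study drug, is essentially unaffected because such events begin on treatment.

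The figures assume a last dose at Week 12 and visits inside their stated windows. A footnote to Appendix 2 accepts visits outside the window, so a late EOT visit would cover somewhat more post-dose time. The ET visit has no fixed window, so the 27-to-30 range applies to completers.

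The prohibited-medication period in 7.3 also has no scheduled check after treatment. That is an inconsistency between 7.3 and the visit schedule which the sponsor has to reconcile; the documents do not show which side was intended.

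**What to change.** 1. Add concomitant medication review to Section 8.4.1 and Appendix 2 at post-treatment week 4.
2. In Section 9.3, change the AE entry limit from 4 weeks to 30 days after the last administration of study drug, matching 10.2.1.2 and 10.6.
3. State that when the week 4 visit falls on days 23 to 29, AEs and medications for the remaining days up to day 30 are collected at post-treatment week 12.
4. Reconcile the prohibited-medication period in 7.3 with the visit schedule. Steps 1 to 3 reach only day 30 and do not settle this.

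The cost is one phrase, one table entry and one extra question at visits already held; no visit is added. The drawback is recall over roughly 7 to 9 weeks for the few days left open by an early week 4 visit. That is weaker than prompt collection but better than no scheduled collection.
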